| PV | Protocol Violation | |
| SAE | Serious Adverse Event | |
| SAP | Statistical Analysis Plan | |
| TEAE | Treatment-Emergent Adverse Event | |
| TESAE | Treatment-Emergent Serious Adverse Event | |
| WHO Drug | World Health Organization Drug Dictionary | |
| VVA | Vulvar and Vaginal Atrophy | |

Statistical Analysis Plan

1 Purpose of Statistical Analysis Plan

The purpose of the statistical analysis plan is to describe in detail all the data, statistical methods, and summary tables required to implement the statistical analysis of Clinical Study Protocol PRG-NY-15-007

.

2 Study Objectives

To demonstrate bioequivalence of Perrigo UK FINCO's Estradiol Vaginal Cream 0.01% compared with ESTRACE (estradiol) Vaginal Cream, USP, 0.01% (Warner Chilcott (US), LLC) in the treatment of vulvar and vaginal atrophy and to demonstrate superiority of the two active treatments over Vehicle.

3 Study Design and Sample Size

3.1 Study Design

The study will be conducted as a double-blind, randomized, parallel-group, vehicle-controlled, multicenter trial.

Each subject will be randomly assigned to one of following treatment groups

s :

- (1) Test: Estradiol Vaginal Cream 0.01%,
- (2) Reference: ESTRACE (estradiol) Vaginal Cream, USP, 0.01%, manufactured by Warner Chilcott (US), LLC
- (3) Vehicle: Vehicle of the test product,

Subjects will be admitted into the study only after written informed consent has been obtained and all of the inclusion and none of the exclusion criteria have been met. Randomization will be performed according to a computer generated randomization scheme where the treatment group designation has been assigned to the subject number. The treatment designation will remain blinded until after the final database is locked. An independent third party generator will generate and hold the randomization code throughout the study. Randomized subjects will apply 2 grams of the assigned treatment once daily intravaginally at bed time for 7 days at approximately the same time each day.

Subjects will come to the study site for clinical evaluations at Visit 1/Screening (Day -14 to Day -1), Visit 2/Randomization (Day 1), and Visit 3/End of Study (Day 8, +3 days) or at early discontinuation.

3.2 Sample Size

subjects will be screened to randomize subjects to obtain mITT subjects and 5

PP subjects.

4 Populations To Be Analyzed

Three subject populations are defined as follows:

- (1) Intent-to-treat (ITT) population: any subject who: (a) was randomized into the study and (b) applied at least 1 dose of assigned study medication intravaginally;
- (2) Modified Intent-to-treat (mITT) population: any subject who (a) was randomized in the study (b) applied at least 1 dose of assigned study medication intravaginally, (c) completed at least one post randomization assessment, and (d) met eligibility criteria;
- (3) Per Protocol (PP) population; any subject who (a) was randomized in the study and met all inclusion/exclusion criteria, (b) had not taken any concomitant medications prohibited by the protocol or had any other significant protocol violations; (c) returned for Visit 3/End of Study within the designated visit window with data on the primary efficacy endpoint and; d) had a study medication application compliance

Study Medication is packaged in blocks of Study medication assignment is blinded.

Of Test:Reference:Vehicle.

5 Planned Analyses

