5.1 Methodological Considerations

All randomized subjects who received study medication will be evaluated for safety. The efficacy analysis will be conducted on both the PP and the mITT populations. No adjustments of p-values for multiple comparisons will be made. No interim analyses are planned. Two-sided hypothesis testing will be conducted for all the tests. Resulting p-values \leq than 0.05 will be considered statistically significant unless noted otherwise. SAS software will be used for all data analyses and tabulations.

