5.2 Handling of Dropouts or Missing Data

Missing efficacy data will be imputed via the LOCF method in the mITT population. For the PP population, subjects who discontinued early due to treatment failure will be considered as non-responders in the primary efficacy endpoint and a treatment failure in the secondary efficacy endpoint while missing values for other efficacy variables will not be imputed.

For demographic and baseline characteristics and the safety profile, each variable will be analyzed using all available data. Subjects with missing data will be excluded only from the analyses for which data are not available.

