Where p_T , p_R and p_V are the proportions of responders at Visit 3/End of Study (Day 8) for the test, reference and Vehicle products, respectively. The tests will be conducted independently for the test product and the reference product using two-sided, $\alpha = 0.05$, continuity-corrected Z-tests. Superiority will be established if the proportion of responders in the active treatment group is greater and statistically different (P \leq 0.05) than that in the Vehicle. Rejection of the null hypothesis supports the conclusion of superiority of the test and reference products over the Vehicle product for the primary efficacy variable.

Superiority analyses will be conducted on both the mITT and the PP populations.

Analysis for bioequivalence will be performed based on the following SAS code (SAS Institute v.9.1.3):

```
The SAS code for p-value (trt=2 for Reference vs. trt=3 for Vehicle): proc freq data=XX; where trt in (2,3); table trt * success /chisq; run;
```

In the mITT population, a LOCF approach will be used to impute missing efficacy data. PP subjects who discontinue due to treatment failure will be included as non-responders for the primary endpoint. No formal statistical analyses are planned to evaluate the consistency of efficacy results across the multiple centers for the primary efficacy variable. These results, however, will be tabulated and, if a center's response is obviously inconsistent with those of the other centers, this will be explored and addressed in the final study report.

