5.6 Safety Variables and Analyses

Duration of Treatment and Medication Compliance

Number of applications, days of exposure, and compliance rate will be summarized by treatment group using descriptive statistics. For each subject, the overall duration of treatment (days) will be calculated using the following formula:

(Date of last application of study medication) - (Date of first application of study medication) + 1.

Medication compliance rate (%) will be calculated for each subject as follows:

(Total number of applications used) / (Expected number of applications) *100%.

Subjects who complete the study are expected to have 7 applications. For prematurely discontinued subjects, expected number of applications will be determined based on the expected number of applications by the time of discontinuation, i.e. the overall duration of treatment. Descriptive summaries of exposure and medication compliance rate will be provided by treatment group for the ITT subjects.

Adverse Events

Adverse events (AEs) will be coded in MedDRA, version 18.1. Treatment-Emergent Adverse Event (TEAE) is defined as any AE occurs on or after application of the first dose of study drug. Number and percent of subjects reporting TEAEs will be tabulated by treatment group. Summaries will be presented by body system and preferred term for the ITT population, and further by severity and relationship to study medication. TEAEs reported by 5% or more subjects for any treatment group will also be summarized. In the summaries of incidence rates (frequencies and percentages) by severity and relationship to study drug, subjects who report more than one event that are mapped to the same preferred term will be counted only once under the strongest severity and relationship, accordingly. Chi-Square or Fisher's exact test will be used to compare the proportions of subjects of the two active treatment groups who report any TEAE.

Treatment-Emergent Serious Adverse Events (TESAEs) will be discussed within the clinical study report. TEAEs, TESAEs and TEAEs that led to treatment interruption or discontinuation will be presented in data listings.

Concomitant Medications, Laboratory Values, and Vitals Signs

Concomitant medications will be coded using the WHO Drug Dictionary, version September 2015, and will be presented in data listings. All laboratory data and vital signs data will be displayed in listings.

Safety comparisons will be performed only for the ITT population.

6 Appendices

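### PP criterion (c) shuts out early treatment-failure dropouts whom Sections 5.2 and 5.5.1 count in PP as non-responders

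*SAP*

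**What the plan says.** Section 4 defines PP by four criteria. Criterion (c) requires that the subject "returned for Visit 3/End of Study within the designated visit window with data on the primary efficacy endpoint". Criterion (d) begins "had a study medication application compliance" and then breaks off at a redaction.

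Section 3.1 fixes the last evaluation as "Visit 3/End of Study (Day 8, +3 days) or at early discontinuation", so the window runs from Day 8 to Day 11 and early discontinuation is named as a separate occasion.

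Section 5.2 states: "For the PP population, subjects who discontinued early due to treatment failure will be considered as non-responders in the primary efficacy endpoint". The same sentence makes these subjects failures in the secondary endpoint. Section 5.5.1 repeats the primary-endpoint rule: "PP subjects who discontinue due to treatment failure will be included as non-responders for the primary endpoint".

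PP matters for the result because, in Section 5.1, "The efficacy analysis will be conducted on both the PP and the mITT populations".

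**The concern.** The population definition and the missing-data rule do not fit together. If criterion (c) is applied as written, a subject who leaves before Day 8 for treatment failure is removed from PP before Section 5.2 can assign her an outcome. That rule then has almost nothing to act on, since a subject with in-window endpoint data needs no assigned outcome.

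Literal exclusion selects on outcome: it removes known non-responders from the denominator and raises the apparent response rate of whichever arm had them. If such dropouts are unbalanced between Test and Reference, the PP difference is biased, in a direction that depends on which arm lost more. A choice between the two PP sets made after unblinding would be open to challenge.

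**Working it through.** **Text check.** Take a subject who stops on, say, Day 5 for treatment failure and has her last visit then.

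| Rule | Outcome for this subject |
|---|---|
| Section 4, criterion (c) | Last visit before Day 8: not in PP |
| Section 5.2 | In PP, non-responder; failure in the secondary endpoint |
| Section 5.5.1 | In PP, non-responder |

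Criterion (d) does not settle the matter by excluding her anyway. Section 5.6 says "For prematurely discontinued subjects, expected number of applications will be determined based on the expected number of applications by the time of discontinuation", so an early dropout can still show high compliance. A subject who stops applying the cream but attends on Day 8 to 11 with data meets (c) and is unaffected.

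**Arithmetic.** No figure in the SAP depends on this point, so there is none to reproduce. The interval and limits are those of Section 5.5.1:

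90% CI = (pT − pR) ± [1.645 × √(pT(1 − pT)/nT + pR(1 − pR)/nR) + (1/nT + 1/nR)/2], with equivalence if it lies within −0.20 to +0.20.

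Arm sizes, response rates and failure counts are assumptions.

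*Worked case: 150 per arm, Reference 90/150 (60%), Test 73 responders, 5 failures in Test only.*

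- Failures counted: pT = 73/150 = 0.4867; difference −0.1133; SE 0.0571; correction (1/150 + 1/150)/2 = 0.0067. CI = −0.1133 ± (0.0940 + 0.0067), or −21.4 to −1.3 points: fail.
- Failures excluded: pT = 73/145 = 0.5034; difference −0.0966; SE 0.0577; correction 0.0068. CI = −19.8 to +0.5 points: pass.

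*All Test responder counts, Reference 90/150:*

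| Failures (Test / Reference) | Fail becomes pass when excluded | Pass becomes fail when excluded |
|---|---|---|
| 1 / 1 | none | none |
| 5 / 5 | none | 105 (upper limit 19.7 becomes 20.05) |
| 2 / 0 | 75 | 105 |
| 5 / 0 | 73–75 | 102–105 (at 102, −1.8 to 17.8 becomes 0.6 to 20.1) |

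*Probability of declaring equivalence in PP.* Each scenario uses 400,000 simulated trials. Each arm is split into responders, failure dropouts and other non-responders.

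| n per arm | True rates, Test vs Reference | Failure dropout | Counted | Excluded |
|---|---|---|---|---|
| 150 | 40% vs 60% | 3.3% both arms | 3.4% | 2.9% |
| 150 | 40% vs 60% | 1.3% Test only | 3.4% | 4.7% |
| 150 | 40% vs 60% | 3.3% Test only | 3.4% | 6.2% |
| 150 | 40% vs 60% | 6.7% Test only | 3.4% | 10.0% |
| 100 | 40% vs 60% | 3.3% Test only | 3.7% | 5.4% |
| 200 | 40% vs 60% | 3.3% Test only | 3.8% | 6.9% |
| 150 | 80% vs 60% | 3.3% Test only | 3.8% | 1.0% |
| 150 | 60% vs 60% | 3.3% both arms | about 92.7% | about 92.0% |
| 150 | 60% vs 60% | 3.3% Test only | 92.7% | 90.4% |

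Rows with a true 20-point difference show false equivalence; rows with equal rates show power. Simulation error is about 0.05 point or less.

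**The case against.** The strongest reply is that the intended rule is not in doubt. Two sections state it for exactly these subjects, and a specific rule normally qualifies a general definition. That stands as a reading of intent. But population flags are programmed from Section 4, and the Section 5.5.1 sentence opens by speaking of subjects already in PP, so it does not clearly override criterion (c).

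Second, the redaction falls inside the PP definition, and an exception could lie there. This cannot be ruled out and limits confidence to medium. However, the visible gap is at the compliance threshold in (d), and (c) itself reads as complete.

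Third, Section 3.1 lists early discontinuation alongside Visit 3, so the end-of-study evaluation might be held then. Even so, an evaluation before Day 8 does not clearly fall within the designated window.

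Fourth, the larger numerical effects need failures in Test and none in Reference. The SAP offers no support for that: both arms are 0.01% estradiol creams applied for 7 days, and failures may be few. This objection stands; the Test-only rows are unfavourable cases.

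Fifth, the modified intent-to-treat (mITT) analysis has no window requirement. That protection is partial, because mITT requires that the subject "completed at least one post randomization assessment". No visit is scheduled between Day 1 and Day 8, so a failure who skips the early-discontinuation visit would normally be missing from both populations.

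**Conclusion.** The inconsistency is real in the visible text and should be fixed. It affects only subjects who discontinue for treatment failure and have no visit from Day 8 to Day 11. With few or balanced failures the practical effect is negligible: one failure per arm changes no verdict in the case examined, and 3.3% dropout in both arms lowers false equivalence slightly. With unbalanced failures and a result near the margin, the two readings can give opposite PP verdicts, and the false-equivalence rate can pass the nominal 5%. These sizes rest on assumed arm sizes, response rates and failure rates. The textual point does not, subject only to what the redacted text may hold.

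**What to change.** Before unblinding, extend PP criterion (c) in Section 4 with an alternative: *or discontinued early due to treatment failure (included as a non-responder)*. Criteria (a), (b) and (d) continue to apply, with compliance computed up to discontinuation as Section 5.6 already provides. This aligns the definition with what Sections 5.2 and 5.5.1 say and alters no visit or clinical rule.

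The cost is one clause; PP responder rates may come out slightly lower than under literal exclusion. If the redacted part of Section 4 already contains the exception, no change is needed.

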5.1 Methodological Considerations

All randomized subjects who received study medication will be evaluated for safety. The efficacy analysis will be conducted on both the PP and the mITT populations. No adjustments of p-values for multiple comparisons will be made. No interim analyses are planned. Two-sided hypothesis testing will be conducted for all the tests. Resulting p-values \leq than 0.05 will be considered statistically significant unless noted otherwise. SAS software will be used for all data analyses and tabulations.

5.2 Handling of Dropouts or Missing Data

Missing efficacy data will be imputed via the LOCF method in the mITT population. For the PP population, subjects who discontinued early due to treatment failure will be considered as non-responders in the primary efficacy endpoint and a treatment failure in the secondary efficacy endpoint while missing values for other efficacy variables will not be imputed.

For demographic and baseline characteristics and the safety profile, each variable will be analyzed using all available data. Subjects with missing data will be excluded only from the analyses for which data are not available.

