5.5 Efficacy Variables and Analyses

5.5.1 Primary Endpoint

The primary endpoint of the study is the proportion of subjects identified as responders at Visit 3/End of Study. A responder is defined as a subject with at least a 25% reduction from baseline (Visit 1/Screening) in the sum of % (percent) basal/parabasal + % (percent) intermediate cells on vaginal cytology AND vaginal pH < 5.0 with a change from Visit 1/Screening vaginal pH of at least 0.5.

Equivalent Efficacy

The compound hypothesis to be tested for clinical equivalence between test and reference is:

$$H_0$$
: $p_T^- p_R^- < -0.20$ or $p_T^- p_R^- > 0.20$ versus

$$\boldsymbol{H}_{\boldsymbol{A}}$$
: -0.20 $\leq \boldsymbol{p}_{\boldsymbol{T}}$ - $\boldsymbol{p}_{\boldsymbol{R}} \leq 0.20.$

Where p_T and p_R are the proportions of responders at Visit 3/End of Study (Day 8) for the test and reference products, respectively. The test product will be considered to be clinically equivalent to the reference product if the 90% CI on the difference in their proportions of responders, calculated by the Wald's method with Yates' continuity correction, is contained within the limits -0.20 to +0.20. Rejection of the null hypothesis supports the conclusion of therapeutic equivalence between the test and reference products for the primary efficacy variable.

Analysis for bioequivalence will be performed based on the following SAS code (SAS Institute v.9.1.3):

P-value is chosen from Continuity Adj. Chi-Square test.

The SAS code for 90% confidence interval (trt=1 for Test, trt=2 for Reference): proc freq data=XX;

```
where trt in (1,2);
tables trt* success / alpha=0.10 riskdiff;
output out=CIDIFF (keep= l_rdif2 u_rdif2 ) riskdiff;
run;
```

For the final 90% continuity-corrected CI, the lower limit = $(1_rdif2 - yates)$ and the upper limit = $(u_rdif2 + yates)$, where yates, the Yates' continuity-correction factor, is derived as (1/n1+1/n2)/2, n1=number of subjects in Test arm and n2=number of subjects in Reference arm.

Superiority

The hypotheses to be tested for superiority of the test and reference products over Vehicle are:

$$H_0: p_T \le p_V \text{ versus } H_A: p_T > p_V$$

$$H_0: p_R \le p_V \text{ versus } H_A: p_R > p_V$$

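### Per-protocol criterion (c) shuts out treatment failures whom SAP sections 5.2 and 5.5.1 say to count as PP non-responders; the mITT rule for missing components also needs one clarifying sentence

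*SAP*

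**What the plan says.** - **Visits (SAP 3.1).** Clinical evaluations are at "Visit 1/Screening (Day -14 to Day -1), Visit 2/Randomization (Day 1), and Visit 3/End of Study (Day 8, +3 days) or at early discontinuation". Treatment lasts 7 days, and no visit is planned between randomization and the end of study.
- **PP population (SAP 4).** Criterion (c) requires that the subject "returned for Visit 3/End of Study within the designated visit window with data on the primary efficacy endpoint". No exception is stated.
- **PP scoring (SAP 5.2).** "For the PP population, subjects who discontinued early due to treatment failure will be considered as non-responders in the primary efficacy endpoint". The same sentence makes them treatment failures for the secondary endpoint and says other missing efficacy values in PP are not imputed. SAP 5.5.1 repeats the primary-endpoint rule and speaks of these subjects as included in PP.
- **mITT population (SAP 4).** Besides randomization, one dose and eligibility, the subject must have "completed at least one post randomization assessment". The type of assessment is not specified.
- **mITT missing data (SAP 5.2 and 5.5.1).** "Missing efficacy data will be imputed via the LOCF method in the mITT population", repeated as "In the mITT population, a LOCF approach will be used to impute missing efficacy data". Neither section gives a treatment-failure rule for mITT.
- **Primary endpoint (SAP 5.5.1).** Response needs at least a 25% cytology reduction from Visit 1, and vaginal pH below 5.0 "with a change from Visit 1/Screening vaginal pH of at least 0.5".

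**The concern.** The treatment-failure rule stands in the section on dropouts and missing data. It is therefore aimed at subjects who left early and may have no Visit 3 result. Criterion (c) keeps out of PP exactly those who were not seen in the window or have no primary data. One section decides how to score subjects whom another section does not admit.

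Sections 5.1 and 5.5.1 use PP alongside mITT for efficacy. If failures are dropped rather than counted, PP responder rates are too high in any arm that has failures, and an imbalance in failures between arms does not show in the PP comparison. Which PP set is built would be settled by whoever programs it rather than by the plan. Section 5.5.2 carries the primary methods over to the secondary endpoint, so the ambiguity extends there.

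The mITT question is smaller. With one post-randomization evaluation, LOCF has little to carry, and the SAP does not say whether a pre-treatment value may be used.

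**Working it through.** The SAP gives no figure on this point, and sample sizes are not legible in the public copy. The check is therefore a comparison of the rules, followed by an illustration on assumed counts.

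**Step 1: apply the rules to each kind of treatment failure.** The window is Day 8, +3 days, that is Day 8 to Day 11.

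| Subject who stops for treatment failure | PP under criterion (c), literally | PP under 5.2 and 5.5.1 | mITT as written (if eligible) |
|---|---|---|---|
| Evaluated before Day 8, data complete | Out | Non-responder | In; scored on her early values |
| No primary endpoint data | Out | Non-responder | In only if some other assessment was done; LOCF |
| Returns Day 8 to 11 with data | In | Non-responder | In; scored on her data |

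The two PP columns agree only in the last row. The first row assumes that an early-discontinuation visit does not itself count as an in-window Visit 3. The wording of 3.1 leaves that open.

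**Step 2: what LOCF does in mITT.** Let S1 and pH1 be the Visit 1 cytology sum and pH.
- Visit 1 cytology carried: (S1 − S1)/S1 = 0%, below 25%. Non-response.
- Visit 1 pH carried: pH1 − pH1 = 0, below 0.5. Non-response.
- Visit 2 symptom score carried: no change from the secondary baseline, so not a success.
- One component missing and the observed one fails: non-response whatever is carried, because both are required.
- One component missing and the observed one passes: non-response if the Visit 1 value is carried; undetermined if pre-treatment values may not be carried.

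The first two lines assume that the last earlier value is the Visit 1 value. The assessment schedule is blank in the public copy, so whether cytology or pH is repeated at Visit 2 is unknown.

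**Step 3: size in PP, all counts assumed.** Take n per active arm with 50% responders, and admit three failures to Test as non-responders. The interval follows 5.5.1: difference ± 1.645·SE, widened on each side by (1/n1 + 1/n2)/2, where SE = √[pT(1−pT)/n1 + pR(1−pR)/n2].

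For n = 100: 50/103 − 50/100 = 0.4854 − 0.5000 = −0.0146. SE = √(0.4854·0.5146/103 + 0.25/100) = 0.0702. Correction = (1/103 + 1/100)/2 = 0.0099. Lower limit = −0.0146 − 1.645·0.0702 − 0.0099 = −0.140.

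| n per arm | Limits before (points) | Difference after | 90% limits after |
|---|---|---|---|
| 100 | ±12.63 | −1.46 | −13.99 to 11.07 |
| 150 | ±10.16 | −0.98 | −11.09 to 9.13 |
| 200 | ±8.72 | −0.74 | −9.43 to 7.95 |

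All stay within ±20 points. With three admitted to each arm the difference stays 0 and both rates fall to 50/103 = 48.5%, 75/153 = 49.0% or 100/203 = 49.3%.

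**The case against.** **The intent is clear.** Section 5.5.1 says these subjects are included, so a sensible programmer would admit them. That shows which way to reconcile the text, but criterion (c) as written still says otherwise. A population definition should not depend on being overridden elsewhere.

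**The rule is not empty.** A subject who stops early but returns in window with data stays in PP, and an early-discontinuation visit might be read as qualifying. This stands. A reader might infer that criterion (c) excludes most treatment failures, but the SAP gives no count, dropout rate or timing to support that.

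**LOCF does little harm.** This also stands. A reader might infer that LOCF in mITT yields wrong results because it can only reach back before treatment. Step 2 shows that a carried Visit 1 value is always non-response, so an explicit non-responder rule gives the same answer. The two differ only for a subject who stopped for treatment failure and yet meets the full responder definition, if the failure rule were extended to mITT.

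**Different rules in mITT and PP are a choice.** The primary endpoint is cytology plus pH. A subject who meets it is a responder as defined, whatever her reason for stopping. Scoring her otherwise in mITT would be for consistency and does not correct a demonstrated error. For scale, with an assumed 100 per arm and 50% response, three such subjects re-scored in Test and none in Reference would give 47% against 50%, a difference of −3.0 points (90% limits −15.6 to 9.6), still inside the margin. That needs three Test subjects who all stopped for failure within a 7-day course and all met every response criterion.

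**Conclusion.** The point holds for PP. Section 4, criterion (c), conflicts with sections 5.2 and 5.5.1 on whether subjects who stop early for treatment failure and lack an in-window Visit 3 with data belong in PP. The conflict rests on legible text. It does not depend on the compliance threshold in criterion (d), which is not readable in the public copy.

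How many subjects it affects is not derivable and is probably small in a 7-day trial. In the assumed illustration the Test–Reference difference moves by 0.7 to 1.5 points with three failures in one arm only, and the equivalence conclusion does not change.

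The mITT part is a clarification only. The documents do not show that LOCF biases the primary result, or that leaving the failure rule out of mITT is a mistake. Nor do they create a need for additional sensitivity analyses on this account.

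**What to change.** 1. **PP definition (SAP 4).** Extend criterion (c) with an alternative such as *or discontinued early because of treatment failure*, so that these subjects enter PP as non-responders (secondary endpoint: treatment failures), as 5.5.1 intends. Check the remaining PP criteria, including compliance and significant protocol violations, and reconcile any that would remove the same subjects.
2. **mITT scoring (SAP 5.2, repeated in 5.5.1).** State that a subject missing a component needed to decide the endpoint is a non-responder (secondary: not a success). State also whether the treatment-failure rule applies in mITT; either answer is defensible if fixed before unblinding.

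The cost is a few sentences in the SAP and matching changes to the population and endpoint programming. No new data or analyses are needed. The downside is slightly lower PP responder rates, for example 48.5% instead of 50% when three failures join an assumed arm of 100.
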